10.2.1.4. Pharmacodynamics

Pharmacodynamic parameters will be evaluated via assessment of post-treatment tumor tissue obtained via voluntary biopsy or resection (Cohorts 1-3), mandatory pre-study and on-treatment biopsies (Cohorts 4 and 5), and blood samples. Parameters evaluated may include localization of glembatumumab vedotin, CR011, or MMAE at the tumor site and/or gpNMB expression levels in serum and tumor tissue, as well as evaluation of other soluble mediators, tumor infiltrating and peripheral leukocytes, circulating tumor cells and other immune response cells of interest such as gpNMB-expressing myeloid-derived suppressor cells, and the effect of CDX-301 on the tumor microenvironment, including the effect on intratumoral dendritic cell populations. (Cohorts 4 and 5). Additional analysis may include immune response assessment to potentially relevant tumor antigens.

10.2.2. Safety Variables

10.2.2.1. Adverse Events: Definition

An adverse event is any untoward medical occurrence in a patient administered a study treatment. An adverse event (AE) can therefore be any unfavorable and unintended sign (including an abnormal laboratory finding), symptom, or disease temporally associated with the use of a study treatment, whether or not related to the study treatment. All observed or volunteered adverse events regardless of suspected causal relationship to the study treatment will be reported, as described in the following sections. For the purposes of this current study, “study treatment” is defined as glembatumumab vedotin and/or: varlilumab, nivolumab, pembrolizumab, or CDX-301.

For all adverse events, the investigator is responsible for obtaining information adequate to determine the:

- appropriate descriptive term: Adverse events should be reported using concise medical terminology, preferably referring to the syndrome/diagnosis rather than symptoms, when possible.

- severity of the event: adverse event severity will be primarily assessed using NCI Common Terminology Criteria for Adverse Events v4.0. (NCI-CTCAE), Version 4.0, division of Cancer Treatment and Diagnosis (DCTD), National Cancer Institute ([Robert, Thomas et al.](#)), National Institute of Health (NIH), Department of Health and Human Services (DHHS) published May 29, 2009 at https://ctep.cancer.gov/protocoldevelopment/electronic_applications/ctc.htm
- onset/resolution dates and outcome
- causality: the relationship of each adverse event to study drug will be defined as “unrelated” or “related” to study treatment:
 - Unrelated: There is little or no possibility that the study drug caused the reported adverse event; and other factor(s) including concurrent illnesses, progression and expression of the disease state, concurrent medications, or a reaction to concurrent medications appear to explain the adverse event.
 - Related: there exists at least a reasonable possibility that the study treatments caused or contributed to the adverse event; an inability to identify an alternate etiology for an adverse event should not, by itself, justify a “related” attribution.
- whether it meets the criteria for classification as a serious adverse event (see [Section 10.2.2.2](#))

The following study-specific points of clarification should be noted when considering adverse event reporting and recording:

- Progression of neoplasia should not be reported as an adverse event or serious adverse event. Findings that are clearly consistent with the expected progression of the underlying cancer should not be reported as an adverse event, and hospitalizations due to the progression of cancer do not necessarily qualify for a serious adverse event. If there is any uncertainty about a finding or event being due solely to progression of neoplasia, the finding or event should be reported as an adverse event or serious adverse event as appropriate. Death due to disease progression occurring within 28 days of study treatment should be reported to Celldex within 24 hours of the site’s awareness of the event; however, these events should not be documented as AEs or SAEs. If there is any uncertainty about the cause of death, the event should be reported as a serious adverse event.
- Withdrawal due to an adverse event should be distinguished from withdrawal due to insufficient response, and recorded on the appropriate adverse event CRF page. For example, if an AE due to recurrence/progression of disease necessitates discontinuation from the study, the primary reason for study discontinuation should be recorded as “Recurrence/Progression of Disease” (not Adverse Event).
- Abnormal objective test findings should be reported as adverse events if the findings are associated with accompanying symptoms, require additional diagnostic testing or medical/surgical intervention, lead to dose modification/discontinuation of study treatment and/or are considered otherwise clinically significant.
- Diagnostic and therapeutic non-invasive and invasive procedures, such as surgery, should not be reported as adverse events. However, the medical condition for which the procedure was performed should be reported if it meets the definition of an adverse event. For

example, an acute appendicitis that begins during the adverse event reporting period should be reported as the adverse event, and the resulting appendectomy should be recorded as treatment of the adverse event.

- Any AEs/SAEs resulting in death should be recorded with an end date equal to the death date, while other events ongoing at the time of death should be recorded with an outcome of “continuing”. If requested, a summary of available autopsy findings should be submitted as soon as possible to Celldex.

10.2.2.2. Serious Adverse Events (SAEs): Definition

An SAE is any adverse event from this study that results in one of the following outcomes:

- Death (any AE that has a fatal outcome must be assigned NCI-CTCAE Grade 5)
- Requires initial or prolonged inpatient hospitalization exceeding 24 hours. As well, any event occurring while the patient is hospitalized which would otherwise require hospitalization or requires transfer within the hospital to an acute/intensive care unit should also be reported under this criterion. This criterion would exclude hospitalization in the absence of a precipitating adverse event, such as admission for treatment of a preexisting condition not associated with a new/worsening adverse event, or admission for elective surgery. As well, admission to rehabilitation/hospice/nursing facilities and outpatient admission for same-day surgeries are not considered “hospitalizations” for the purpose of this criterion.)
- Is life-threatening (An AE is considered "life-threatening" if, in the view of either the investigator or sponsor, its occurrence places the patient at immediate risk of death. It does not include an AE or suspected adverse reaction that, had it occurred in a more severe form, might have caused death.)
- Is a persistent or significant disability/incapacity, or substantial disruption of the ability to conduct normal life functions
- Congenital anomaly/birth defect
- Other significant medical hazard (Medical and scientific judgment should be exercised in determining whether an event is an important medical event. An important medical event may not be immediately life-threatening and/or result in death or hospitalization. However, if it is determined that the event may jeopardize the patient and/or may require intervention to prevent one of the other adverse event outcomes, the important medical event should be reported as serious. Examples of such events are intensive treatment in an emergency room or at home for allergic bronchospasm; blood dyscrasias or convulsions that do not result in hospitalization; or development of drug dependency or drug abuse.)

The following study-specific points of clarification should be noted when considering serious adverse event reporting and recording:

- Progression of neoplasia should not be reported as an adverse event or serious adverse event. Findings that are clearly consistent with the expected progression of the underlying cancer should not be reported as an adverse event, and hospitalizations due to the progression of cancer do not necessarily qualify for a serious adverse event. If there is any uncertainty about a finding being due solely to progression of neoplasia, the finding should

be reported as an adverse event or serious adverse event as appropriate. Death due to disease progression occurring within 28 days of study treatment should be reported to Celldex within 24 hours of the site's awareness of the event; however, these events should not be documented as AEs or SAEs. If there is any uncertainty about the cause of death, the event should be reported as a serious adverse event.

10.2.2.3. AE/SAE Reporting

The investigator is to report all directly observed AEs and all AEs spontaneously reported by the study patient. In addition, each study patient will be questioned about AEs.

AEs and SAEs should be recorded on the CRF from the time the patient has taken at least one dose of study treatment through (whichever occurs first) either: a) 28 calendar days after the last administration of glembatumumab vedotin or 70 calendar days after the last administration of varlilumab (the latter whichever occurs later, Cohort 2); 70 days after last dose of the PD-1 targeted checkpoint inhibitor (the latter whichever occurs later in Cohorts 3 and 5); 28 calendar days after the last administration of CDX-301 (the latter whichever occurs later, Cohorts 4 and 5); or b) initiation of alternate anticancer therapy.

However:

- Any SAE occurring any time after the reporting period must be promptly reported if a causal relationship to study treatment is suspected
- For AEs or SAEs with a causal relationship to the investigational product, follow-up by the investigator is required until the event or its sequelae resolve to \leq Grade 1, or stabilize for at least three months after the last administration of study treatment (whichever is sooner).

All AEs will be reported on the AE page(s) of the CRF, while SAEs will also be reported in an expedited fashion using the SAE Report. The AE CRFs and SAE Reports must be completed in a consistent manner; for example, the same AE term, causality, severity, and onset/resolution dates should be used on both forms.

In case of an SAE (regardless of causality), an SAE Report must be completed and submitted to Celldex within 24 hours of the site's notification of the event, irrespective of the extent of available adverse event information. This timeframe also applies to additional new information (follow-up) on previously forwarded SAE reports. The investigator is obligated to pursue additional information required for thorough evaluation of each SAE as may be requested by Celldex.

Serious adverse event reporting to regulatory authorities and all participating investigators will be conducted by Celldex in accordance with 21CFR312.32 and international regulations, as appropriate.

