
Eligibility Criteria
	
Inclusion Criteria
 
Patients may be included in the study only if they meet all of the following inclusion criteria at the time of study enrollment:
 
 1. Read, understood, and provided written informed consent and, if applicable, Health Insurance Portability and Accountability Act (HIPAA) authorization after the nature of the study has been fully explained and must be willing to comply with all study requirements and procedures 2. Advanced (unresectable Stage III or Stage IV) histologically-confirmed melanoma 3. Documented progressive disease, based on radiographic, clinical or pathologic assessment, during or subsequent to the last anticancer therapy. For Cohorts 3 and 5, progression (confirmed from two scans at least 4 weeks apart) must have occurred during the PD-1 targeted CPI treatment and the investigator has deemed it appropriate to continue to treat beyond confirmed disease progression. 4. No more than 1 prior chemotherapy-containing regimen for advanced disease. For Cohorts 1, 2, and 4, prior treatments received must include at least one check-point inhibitor (e.g., anti-CTLA-4-, PD-1-, PD-L1-targeted immunotherapy) and for patients with a BRAF mutation, at least one BRAF- or MEK-targeted therapy, unless patients are not candidates for, or refused, these therapies. For Cohorts 3 and 5, prior treatment received must include a PD-1 targeted CPI (i.e., nivolumab or pembrolizumab) administered during the most recent disease progression and for patients with a BRAF mutation, at least one BRAF- or MEK-targeted therapy when appropriate. 5. Pre-treatment tumor tissue, and for Cohorts 2 and 3 a skin fold biopsy, available for retrospective evaluation of gpNMB in tumor or normal epithelial cells, respectively, by central immunohistochemistry (IHC): 
 a. All patients in Cohorts 1-3 must submit an archival formalin-fixed and paraffin-embedded (FFPE) tumor tissue sample representative of advanced (Stage III or IV) disease, obtained more than 12 weeks prior to study entry (Historic sample). b. All patients in Cohorts 1-3 are also required to submit a second, recently-obtained FFPE tumor tissue sample (Pre-entry sample). Tissue should be obtained within the 12 weeks prior to study entry, be subsequent to the last systemic anticancer therapy received, and be post-tumor progression. c. All patients in Cohorts 4-5 are required to submit a fresh Pre-entry tumor tissue sample as well as a fresh On-treatment tumor tissue sample. Pre-entry tissue should be obtained within the 12 weeks prior to study entry, be subsequent to the last systemic anticancer therapy received, and be post-tumor progression. Tumor tissue samples will be collected until such time Celldex informs the sites that further data is not needed. 
For patients who need to undergo a new biopsy to obtain a Pre-entry, or both Pre-entry and On-treatment sample, biopsy sites must be soft tissue or visceral

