7.2.2. Subject Eligibility

7.2.2.1. Inclusion Criteria

Patients may be included in the study only if they meet all of the following inclusion criteria at the time of study enrollment:

1. Read, understood, and provided written informed consent and, if applicable, Health Insurance Portability and Accountability Act (HIPAA) authorization after the nature of the study has been fully explained and must be willing to comply with all study requirements and procedures.
2. Advanced (unresectable Stage III or Stage IV) histologically-confirmed melanoma.
3. Documented progressive disease, based on radiographic, clinical or pathologic assessment, during or subsequent to the last anticancer therapy. For Cohorts 3 and 5, progression (confirmed from two scans at least 4 weeks apart) must have occurred during the PD-1 targeted CPI treatment and the investigator has deemed it appropriate to continue to treat beyond confirmed disease progression.
4. No more than 1 prior chemotherapy-containing regimen for advanced disease. For Cohorts 1, 2, and 4, prior treatments received must include at least one check-point inhibitor (e.g., anti-CTLA-4-, PD-1-, PD-L1-targeted immunotherapy) and for patients with a BRAF mutation, at least one BRAF- or MEK-targeted therapy, unless patients are not candidates for, or refused, these therapies. For Cohorts 3 and 5, prior treatment received must include a PD-1 targeted CPI (i.e., nivolumab or pembrolizumab) administered during the most recent disease progression and for patients with a BRAF mutation, at least one BRAF- or MEK-targeted therapy when appropriate.
5. Pre-treatment tumor tissue, and for Cohorts 2 and 3 a skin biopsy, available for retrospective evaluation of gpNMB in tumor or normal epithelial cells, respectively, by central immunohistochemistry (IHC):
 - a. All patients in Cohorts 1-3 must submit an archival FFPE tumor tissue sample representative of advanced (Stage III or IV) disease, obtained more than 12 weeks prior to study entry (Historic sample).
 - b. All patients in Cohorts 1-3 are also required to submit a second, recently-obtained FFPE tumor tissue sample (Pre-entry sample). Tissue should be obtained within the 12 weeks prior to study entry, be subsequent to the last systemic anticancer therapy received, and be post-tumor progression.
 - c. All patients in Cohorts 4-5 are required to submit a fresh Pre-entry tumor tissue sample

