as well as a fresh On-treatment tumor tissue sample. Pre-entry tissue should be obtained within the 12 weeks prior to study entry, be subsequent to the last systemic anticancer therapy received, and be post-tumor progression. Tumor tissue samples will be collected until such time Celldex informs the sites that further data is not needed.

For patients who need to undergo a new biopsy to obtain a Pre-entry, or both Pre-entry and On-treatment, sample, biopsy sites must be soft tissue or visceral tumor lesions that can be biopsied with acceptable clinical risk (as judged by the investigator). The biopsy site chosen should have not been previously irradiated. Biopsy sites must be distinct from RECIST 1.1 target lesions, unless, in the case of the Pre-entry biopsy, the biopsy is obtained more than 10 days prior to the Screening Disease Assessment. Patients must be separately consented for collection of a fresh Pre-entry, or both Pre-entry and On-treatment sample.

- d. All patients in Cohorts 2 and 3 must agree to submit a recently-obtained FFPE skin fold (axilla or groin) biopsy (Pre-entry sample). Tissue may be obtained by punch biopsy or surgical excision. Skinfold biopsies will be collected until such time Celldex informs the sites that further data is not needed.

NOTE: Patients who cannot fulfill the requirement for either the Historic, Pre-entry, or On-treatment sample submission in Cohorts 1-5 may be enrolled in the study with prior permission of the Celldex Medical Monitor. In no case will a patient be allowed to enter the study without at least one available tumor sample.

6. Male or female patient ≥ 18 years of age
7. Eastern Cooperative Oncology Group (ECOG) Performance Status 0 to 1 ([Appendix 4](#))
8. Life expectancy of ≥ 12 weeks
9. Measurable (target) disease by RECIST 1.1 criteria ([Eisenhauer, Therasse et al. 2009](#)) ([Appendix 3](#)). Target lesions selected for tumor measurements should be those where additional (e.g., palliative) treatments are not indicated or anticipated.
10. Resolution of toxicities related to prior therapies (including radiotherapy) to \leq NCI-CTCAE Grade 1 severity, except for alopecia, grade 2 fatigue, vitiligo, or endocrinopathies on replacement therapy
11. Screening laboratory values must meet the following criteria:
 - Absolute neutrophil count (ANC) $\geq 1500/\text{mm}^3$
 - Hemoglobin ≥ 9.0 g/dL
 - Platelet count $\geq 100,000/\text{mm}^3$

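### Adverse events from protocol-required biopsies taken after consent but before the first dose are not recorded or expedited as AEs or SAEs

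*Protocol*

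**What the plan says.** **When recording starts.** Protocol 10.2.2.3 states that "AEs and SAEs should be recorded on the CRF from the time the patient has taken at least one dose of study treatment". The definition in 10.2.2.1 agrees: "An adverse event is any untoward medical occurrence in a patient administered a study treatment", and that section defines study treatment as the drugs alone. Section 10.2.2.2 defines an SAE as an adverse event with a serious outcome. The expedited rule in 10.2.2.3 reads "In case of an SAE (regardless of causality), an SAE Report must be completed and submitted to Celldex within 24 hours" of the site's learning of it.

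**What is done before dosing.** Inclusion criterion 5 (Protocol 7.2.2.1) says "All patients in Cohorts 4-5 are required to submit a fresh Pre-entry tumor tissue sample", together with an on-treatment sample. Patients in Cohorts 1-3 must supply recent tumor tissue, and those in Cohorts 2-3 a skinfold biopsy. Where a new tumor biopsy is needed, "biopsy sites must be soft tissue or visceral tumor lesions that can be biopsied with acceptable clinical risk", and collecting a fresh sample requires separate consent.

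**Patients not enrolled.** Under 10.1.2, patients who are screened but do not meet all entry criteria are left out of the clinical database.

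**The concern.** The protocol asks patients to undergo an invasive procedure, possibly of a visceral lesion, for research purposes, and treats it as carrying enough risk to need its own consent. Yet AE recording opens only when drug is given. Bleeding, infection or a pneumothorax after a study biopsy could put a patient in hospital without meeting the protocol's definition of an adverse event. A complication bad enough to make the patient ineligible would leave nothing in the database.

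What is at stake is the completeness of the record of harm from procedures that the trial itself requires. An absence of pre-dose biopsy events in the AE data would carry no information, because none could be entered. The sponsor also decides how long tissue collection continues, and would do so without that part of the procedural safety record.

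**Working it through.** The plan states no figure on this point, so the check is mainly one of text and timing.

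**1. Does any clause reach an event between consent and first dose?**
- *AE definition (10.2.2.1):* no. The patient must already have received a study drug.
- *SAE definition (10.2.2.2):* no. An SAE is a kind of AE, so it inherits the same condition.
- *24-hour rule (10.2.2.3):* it disregards causality, but it applies to SAEs as defined.
- *Extension of the window (10.2.2.3):* the only one runs forward in time and concerns the drug: "Any SAE occurring any time after the reporting period must be promptly reported if a causal relationship to study treatment is suspected".
- *Rapid notification list (10.2.2.4):* it adds potential treatment-limiting toxicity, death from progression, overdose and pregnancy, but no procedural events.
- *Schedules of assessments:* neither has AE monitoring at Screening. It begins at Cycle 1 Day 1 in Table 1 (Cohorts 1-3) and in the Day -6 to -2 column, with the first CDX-301 dose, in Table 2 (Cohorts 4-5).

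**2. When do the biopsies happen?**
- Study-specific procedures follow consent (footnote 2 of both tables), so a biopsy done for the study before dosing lies between consent and first dose.
- Screening runs from Day -28 to Day -1 in Cohorts 1-3 and from Day -35 to Day -7 in Cohorts 4-5. Pre-entry tissue may be up to 12 weeks old at entry. AE recording covers none of this period.
- The on-treatment biopsy in Cohorts 4-5 is set for Cycle 1 Day 7, give or take a day (Table 2, footnote 8). That is after the first dose, and AE monitoring is scheduled at the visit. Its complications are captured.

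**3. How many patients could an amendment still help?** Planned numbers are from the protocol synopsis.
- Cohorts 4 and 5, fresh pre-entry tumor biopsy: 10-12 + 30 = 40-42 dosed patients. This is a ceiling, because the Medical Monitor may permit entry without a given sample and the sponsor may end collection. If Cohort 5 does not open, the ceiling is 10-12.
- Cohort 3: about 30 are planned. The documents do not say how many remain to be enrolled, or how many would need a new tumor biopsy.
- Cohorts 1 and 2: described as already enrolled, so their pre-dose biopsies are past.
- Patients biopsied but never dosed are additional. Their number is not given.

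**4. Illustration only.** The documents give no complication rate. If 1% to 5% of pre-dose tumor biopsies led to a serious event (an assumption), the expected number in Cohorts 4-5 would be between 0.01 × 40 = 0.4 and 0.05 × 42 = 2.1. Without Cohort 5 it would be between 0.01 × 10 = 0.1 and 0.05 × 12 = 0.6. The gap in the text does not depend on any such rate.

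**The case against.** The rule is consistent. The definition, the reporting window, both schedules and the treatment-emergent definitions (Protocol 11.5.3, SAP 9.2.1) all begin at first dose, which suits a study of drug toxicity. A pre-dose biopsy event should be kept out of the treatment-emergent tables and treatment-limiting toxicity counts, and it has no bearing on ORR. All of this stands.

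A reader might infer that complications of mandated biopsies are never captured at all. The documents do not support that:
- The second mandatory biopsy in Cohorts 4-5 falls inside the window, so the decision on Cohort 5 would have on-treatment biopsy data from Cohort 4.
- For treated patients, a pre-dose event may appear when medical history is updated before dosing (footnote 10 of both tables), or through concomitant medication, recorded from 28 days before treatment (Protocol 9).
- An event that worsens after first dose counts as treatment-emergent under SAP 9.2.1.

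These routes soften the gap but do not close it. None carries a 24-hour report or a judgment of relation to the procedure, the medication record reaches back only 28 days against a 12-week tissue window, and none helps for patients who fail screening.

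A reader might also infer that new biopsies are common in Cohorts 1-3. That is not supported either: existing recent tissue can qualify, the documents do not say how often it does, and skinfold collection can be stopped.

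Finally, consent pages were removed from the review copy, so procedural risk may be addressed there. Consent wording would not by itself change the reporting rule in 10.2.2.3.

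**Conclusion.** The point holds in limited form. Followed exactly, 10.2.2.1 and 10.2.2.3 leave AEs and SAEs caused by protocol-mandated biopsies after consent and before first dose unrecorded and unexpedited as such, and 10.1.2 removes any database trace in screen failures. The patients who can still benefit are at most about 40-42 dosed patients in Cohorts 4-5, any remaining Cohort 3 patients who have a skinfold or newly required tumor biopsy, and an unknown number biopsied but never dosed. This assumes that the planned enrollment is reached and that Cohort 5 opens. The number of events cannot be derived from the documents and is probably small. This is a gap in safety reporting that is cheap to close; it does not threaten the ORR, treatment-limiting toxicity or treatment-emergent analyses.

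**What to change.** Add one sentence to Protocol 10.2.2.3: from informed consent onward, any SAE judged related to a protocol-mandated procedure is recorded and reported to the sponsor within 24 hours, including in patients who fail screening or are never dosed. Align the definition in 10.2.2.1 so that such an event qualifies, and provide a place to record it for patients whom 10.1.2 keeps out of the clinical database. List these events separately from treatment-emergent AEs. Leave the rest of the AE window and all analysis definitions unchanged.

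The cost is a short amendment and a small amount of extra reporting. The benefit is prospective only: Cohorts 4-5 and whatever remains of Cohort 3.
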